*Principal investigator

** Sponsor

SECTION 1

1. Introductory Statement

Title: Autologous Cardiac Stem Cell Injection in Patients with Hypoplastic Left Heart Syndrome: An Open Label Pilot Study. (CHILD Study)

Sponsor: [name].
Interdisciplinary Stem Cell Institute
University of Miami Miller School of Medicine,
Division of Cardiology, Miami, Florida

Cell Manufacturing Center:
Interdisciplinary Stem Cell Institute
Clinical Research Cell Manufacturing (CRCMP) Program
University of Miami Miller School of Medicine
[name]
[name]

Test Agent: Autologous c-kit-positive cells (c-kit⁺ cells)

Population: Male or female neonates diagnosed with hypoplastic left heart syndrome (HLHS) undergoing Stage I Norwood operation.

Sample Size: A total of 32 subjects will be enrolled for this pilot study in a staged enrollment.

Treatment: All subjects with the diagnosis of hypoplastic left heart syndrome (HLHS) undergo a palliative reconstructive surgery performed in the first two weeks of life, termed the Norwood procedure. The Norwood procedure involves reconstruction of the aortic arch, resection of the atrial septum, and establishment of pulmonary blood flow through either a modified Blalock-Taussig shunt (mBTS) (a Gore-Tex tube from the innominate artery to the right pulmonary artery) or a Sano shunt (a Gore-Tex tube from the right ventricle to the right pulmonary artery). To initiate cardiopulmonary bypass for this surgery, the right atrial appendage is cannulated. Typically, the appendage is excised and discarded during this step. However, in our study, this excised right atrial appendage will be harvested and c-kit⁺ cells will be isolated. The process and manufacturing of the c-kit⁺ cells will be exactly as specified in the TAC-HFT II Study (IND# 14647, NCT00768066). TAC-HFT II was a Phase I/II, Randomized, Placebo-Controlled Study of the Safety and Efficacy of Transendocardial Injection of Autologous Human Cells (Mesenchymal or the combination of MSC and ckit+ in Patients with Chronic Ischemic Left Ventricular Dysfunction and Heart Failure Secondary to Myocardial Infarction trial of University of Miami under IND #14647. The patients will then proceed with the typical postoperative care. The second stage in the palliation of HLHS is a scheduled bidirectional cavopulmonary anastomosis, BDCPA) operation that

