Primary: Consistent with the nature of this study, multiple assessments will be performed to evaluate the safety, feasibility, and efficacy of intramyocardial delivery of c-kit⁺ cells in subjects with HLHS:

1. Safety will be assessed by monitoring the following major adverse cardiac events during the first 30 days post Stage II BDCPA operation:

- Greater than 30 seconds of sustained/symptomatic ventricular tachycardia requiring intervention with inotropic support or anti-arrhythmics
- Cardiogenic shock (i.e. tissue hypoperfusion presented by hypotension due to decreased cardiac output, determined by rising lactate levels (5x normal levels in first 24 hours, 2.5x normal levels in first 30 days)
- Unplanned cardiovascular operation due to right ventricular intramyocardial injection site bleeding in the first 5 days after Stage II BDCPA operation
- Need for new permanent pacemaker
- Stroke or embolic event to the brain determined by CT scan
- Death

2. Feasibility will be assessed by monitoring how many c-kit+ products can be manufactured and delivered to subjects and how many subjects can get baseline, 6-month and 12-month MRIs.
3. Efficacy will be assessed at 12 months post-Stage II BDPCA operation by change from baseline in right ventricular ejection fraction, right ventricular end-diastolic volume, right ventricular end-systolic volume, and tricuspid regurgitation measured by serial echocardiograms and MRI scans (baseline, 6 months and 12 months).

Secondary:

1. Incidence of mortality or need for transplantation after the Stage II BDCPA operation up to 12-month follow-up.
2. Incidence of the following after the Stage II BDCPA operation up to 12-month follow-up:
 - i. All-cause mortality
 - ii. Cardiovascular mortality
 - iii. Need for transplantation
 - iv. Hospitalization for heart failure
 - v. Cardiovascular morbidity, including myocardial infarction, stroke, heart failure, or sustained/symptomatic arrhythmias
3. Changes in somatic growth velocity (weight, length, head circumference) over 12 month follow-up.
4. Change in quality of life measured by the Infant Toddler Quality of Life Survey (ITQOL) at baseline, 6 and 12 months after Stage II BDCPA operation.

2. General Investigational Plan

A. Background

Surgical and Clinical Outcomes for HLHS

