We plan to enroll thirty-two patients with HLHS in a two staged enrollment process. In this study, a maximum of 21 patients will receive intramyocardial injection of c-kit⁺ cells and 11 standard of care control patients with no injection. The enrollment of the patients will occur in two staged groups: Group A and Group B. Initially in Group A, 10 consecutive HLHS patients will be enrolled in the c-kit⁺ cell treatment arm to determine feasibility and safety. Six months after the last patient is enrolled in Group A, the DSMB will conduct a review of all Group A patients in order to determine whether the methodology is feasible and safe, including the harvesting, processing, and administering of the c-kit⁺ cells. Thereafter, Group B will enroll a total of 22 HLHS patients which will be randomized, double-blinded to the treatment and standard of care control arms in a 1:1 ratio, respectively, in order to have 11 c-kit⁺ cell-treated patients and 11 control patients. Randomization will occur post-Norwood operation upon receipt of viable tissue sample at University of Miami Clinical Research Cell Manufacturing Program (CRCMP). The rationale underlying this two-staged enrollment is to initially test the feasibility and safety of this methodology of obtaining the c-kit⁺ cells from the right atrial appendage with the Group A patients. The second Group B patients may provide the required numbers to potentially validate the efficacy of the trial. Eventually, a Phase II trial will provide the necessary numbers to provide an accurate assessment of efficacy of the c-kit⁺ cells in HLHS patients.

B.1.2. Sample Size

Twenty-one (21) subjects will be enrolled in the treatment group and eleven (11) in the standard of care control group. The 10 Group A subjects are part of an open-label safety and feasibility analysis. The 22 Group B subjects will be randomized 1:1 to cell treatment and control to detect a difference of 6 RVEF units, given a standard deviation of 4, 89% power and type 1 error of 0.05. Twenty patients are needed with 10% added for possible lost to follow-up.

B.1.3. Dosage and Administration

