Prior to the Stage I Norwood operation, the subject's guardians will be given a complete explanation of the purpose of the study and evaluations to be performed which are in addition to those of standard of care. The Institutional Review Board (IRB) approved informed consent document will be reviewed with the guardians and any questions answered at that time.

The consent document (and the discussion with the guardians) will clearly outline the following:

- 1) the subject's guardians do not have to consent to this research for their child to receive the planned surgeries,
- 2) if the guardians want the subject to participate, there is a need for tissue sample collection to take place at the time of the Stage I Norwood operation (to enable study product to be manufactured) and consent is needed for this, if the subject is randomized to the standard of care group (i.e. no cells to be delivered) then the tissue will be discarded at the manufacturing facility.
- 3) there is a potential that the subject could be deemed ineligible for study participation prior to the Stage II BDCPA operation; for example, due to changes in health status, and
- 4) what a change in participation status would mean for any acquired tissue if the subject is discontinued from the protocol prior to the Stage II BDCPA operation.

Should the guardians consent to the study, a copy of the signed consent form will be provided to them at that time.

Prior to the Stage II BDCPA operation, the subject's guardians will be contacted to schedule appointments for research-related testing needed for determining continued eligibility. Before any testing is initiated, the consent form will be re-reviewed with the guardians to affirm their continued willingness to allow their child to participate. This re-review will be documented in the subject's chart. If the guardians are no longer interested in participation, the subject will be withdrawn from the study, and this will be noted in the subject's chart.

B.3.2. Screening Phase Assessments

The Screening Phase starts at enrollment and completes at the initiation of the harvest during the Stage I Norwood operation. The screening phase may last between 2 – 3 weeks, and will not alter the patient's pre-surgical duration.

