- i. Collection of Blood for Biomarker analysis of circulating pro-inflammatory markers (see MOP for blood collection and shipping instructions to CRCMP)

The research-only assessments listed above are the cMRI, ITQOL survey, and biomarker blood sample tests thus AE monitoring will begin when the first of these is performed.

B.3.3.d. Study Product Injection

The Stage II BDCPA operation occurs between 4 to 6 months of age. For Group B subjects randomized to study treatment, during this surgery when the patient is on cardiopulmonary bypass, the previously harvested c-kit⁺ cells will be injected into the right ventricle directly intramyocardially using a 25-27gauge needle syringe at the completion of the repair but before separating from cardiopulmonary bypass. The entire dose of the cells, up to 12,500/kg patient weight in 600 microliters, will be divided and delivered in 6-10 intramyocardial injections. The intramyocardial injection of cells will take approximately 5-10 minutes, which is insignificant to the total bypass time. The remaining part of the operation will proceed as anticipated.

B.3.3.e. Investigational Final Product Preparation

The harvested c-kit⁺ cells will undergo quality control testing and review by CRCMP laboratory director and quality assurance manager prior to release for clinical use. When the Stage II BDCPA operation is scheduled for subjects randomized to receive study product, upon request from the clinical site, product is shipped cryopreserved from CRCMP to the local cell processing laboratory in a validated vapor phase cryoshipper maintained at temperatures < -120 °C with a temperature monitoring device. Upon arrival, product is inspected to ensure that product is in good condition and the temperature data will be verified before transferring to the secured vapor phase storage freezer at the site. In the event that the temperature deviates from the specified shipping temperature, the product will not be used. Local cell processing laboratory notify CRCMP. The incident will be investigated with corrective and preventive actions implemented following the CRCMP standard operating procedures. CRCMP will prepare a new shipment of the product.

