Potential risks related to cell processing include the risk of infusion of bacterially contaminated cells that may cause infection. There is the potential for infusion of

foreign proteins that are residual process components, which may evoke an immune response.

D.4.2. Potential Risks of Cell Therapy Delivery

As with any new drug, an allergic reaction could occur. This could result in hives, rash, difficulty breathing or collapse of the lung and breathing systems. These reactions are usually reversible but could lead to permanent disability or death. Other rare but possible risks include infection, respiratory distress or failure, pulmonary edema, renal or hepatic failure. As with any investigational drug, administration of autologous c-kit-positive cells could cause currently unknown side effects that might be permanently disabling or fatal, including tumor formation or arrhythmias.

The c-kit⁺ cells will be delivered through intramyocardial injection. Risks associated with intramyocardial injection into cardiac tissue include possible sustained rapid heart rates and ventricular arrhythmias, ectopic tissue formation, cardiac perforation, infections and abnormal laboratory values. Additional risks associated with the delivery are minimized due to the nature of the study agent, namely autologous stem cells. It is possible that a small amount of cells will enter the systemic circulation of the heart rather than the myocardium, although since these are autologous cells there should be no sequelae of such an event.

D.4.3. Potential Risks of MRI Study

The risks associated with the MRI study with gadolinium include anesthetic risks, anaphylactoid reaction, arrhythmia, vasodilation, and nephrogenic systemic fibrosis. At Children's Memorial Hospital, the University of Maryland, a study was conducted that has shown no complications with the MRI study in congenital heart patients during the last nine years. This protocol is mentioned below.

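### The bleeding item in the primary safety list can occur only in injected infants, so it is zero by definition in the 11 controls and should not be compared between arms or pooled over all 32 subjects

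*Combined protocol and SAP*

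**What the plan says.** The Introductory Statement (Endpoints, Primary, item 1) assesses safety by monitoring "major adverse cardiac events during the first 30 days post Stage II BDCPA operation". One listed event is "Unplanned cardiovascular operation due to right ventricular intramyocardial injection site bleeding in the first 5 days after Stage II BDCPA operation". The others are ventricular tachycardia needing intervention, cardiogenic shock, a new permanent pacemaker, stroke or cerebral embolism, and death.

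B.1.1 plans at most 21 injected infants (10 in Group A and 11 in Group B) and "11 standard of care control patients with no injection". The consent section (B.3.1) confirms that controls are given no cells. No sham injection is described anywhere. C.2 defines the Safety Analysis Set as all Group A and all randomised Group B subjects and assigns the primary safety analysis to it.

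Under B.3.3.d the cells "will be injected into the right ventricle directly intramyocardially using a 25-27gauge needle syringe at the completion of the repair", in treated infants only. Under B.3.3.e the site requests product for infants randomised to receive it, and the principal investigator sends a request to the local cell laboratory before the operation. B.1.1 calls Group B "randomized, double-blinded to the treatment and standard of care control arms in a 1:1 ratio", while the title reads "An Open Label Pilot Study".

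**The concern.** The other events in the list can occur in either arm. This one needs an injection site, which controls do not have. A control re-explored for bleeding on day 2 does not meet the item, while a treated infant with the same re-operation may meet it. The randomised control arm therefore gives this item no concurrent rate against which to read a treated event.

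Among treated infants, the words requiring the operation to be due to injection-site bleeding oblige someone to name a source. The documents do not say who does so, by what criteria, or whether without knowledge of the arm. At stake is how a handful of events is read in a study whose first objective is the feasibility and safety of the injection. In an arm of 11, one event is 1/11 = 9.1 percentage points.

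**Working it through.** The plan states no event rate, margin or power for the safety list, so there is no figure to reproduce. The check sets the sections side by side and then shows the size of the effect.

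**Who can have the event.** Injected: 10 + 11 = 21. Not injected: 11. Safety Analysis Set as planned: 21 + 11 = 32. The control count for this item is 0/11 whatever the true rate of re-operation for bleeding in controls. One event pooled over the set is 1/32 = 3.1%; among those who can have it, 1/21 = 4.8%.

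**Who attributes the source.** C.3 describes adverse event tabulation. D.2.3 gives the medical monitor the task of deciding on expedited reporting. D.6 describes unblinded review by the monitoring board. None of these sections sets criteria for bleeding source or provides endpoint adjudication. B.3.3.d and B.3.3.e make it likely that the team at a re-operation would know whether injections had been made. That is an inference; no section says who attributes the source.

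**Illustration: background bleeding.** The documents give no rate. Assume that 2% to 10% of infants are re-operated for bleeding from any source within 5 days, equally in both arms.
- Controls, expected number: 11 × 0.02 = 0.22 to 11 × 0.10 = 1.1. Chance of at least one: 1 − 0.98^11 = 20% to 1 − 0.90^11 = 69%. All would score zero on this item.
- Injected, expected number: 21 × 0.02 = 0.42 to 21 × 0.10 = 2.1. Each would be counted or not according to the source named.

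**Illustration: effect on an any-event rate, if one were formed.** Let q be the rate of the other listed events (assumed 10%), b the rate of bleeding re-operation unrelated to the cells and equal in both arms, and a the share of these attributed to an injection site. Assume that bleeding and the other events are independent. Controls have rate q. Treated infants have 1 − (1 − q)(1 − ab).

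| b | Control, as written | Treated, as written (a = 0 to a = 1) | Both arms, any bleeding re-operation counted |
|---|---|---|---|
| 2% | 10.0% | 10.0% to 11.8% | 11.8% |
| 5% | 10.0% | 10.0% to 14.5% | 14.5% |
| 10% | 10.0% | 10.0% to 19.0% | 19.0% |

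For example, at b = 10% and a = 1: 1 − 0.90 × 0.90 = 19.0%. At a = 0, which is correct attribution under these assumptions, the arms agree. The artificial difference comes from misattribution, not from the zero in controls alone.

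**What a test would show, if one were run.** For k treated events against 0 in 11 versus 11, Fisher's two-sided p is 2 × C(11,k)/C(22,k): 1.00 for k = 1, 0.48 for k = 2 and 0.035 for k = 5. The item matters for description and judgement, not for significance.

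**The case against.** The strongest reply is that the item is meant to measure harm caused by the injection, for which zero is the right value in uninjected infants. In Group A, which has no controls, an injection-specific item is easier to interpret than bleeding from any cause. This stands, and it is why the source should be kept as a sub-item.

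A reader might go further than the documents allow in four ways.
- **That the between-arm safety comparison is biased by construction.** The plan defines no any-event variable and no between-arm safety test. C.3 is descriptive, and the chi-square or Fisher line sits under bioactivity in C.5. Bias needs misattribution, and it can run either way: background bleeding blamed on an injection site counts against the cells, while injection-site bleeding assigned elsewhere hides harm.
- **That the control arm cannot supply a background rate at all.** Table 1 schedules adverse event monitoring without regard to arm, and D.2.1 makes prolonged hospitalisation a criterion for seriousness. Control re-operations should therefore be recoverable. D.2 words the adverse event definition around subjects given product, but the same section has investigators note all events from the consent re-review at baseline. What is missing is a place for control re-operations in the primary list.
- **That perforation managed without an operation goes unrecorded.** D.4.2 names among the injection risks "ectopic tissue formation, cardiac perforation, infections and abnormal laboratory values". Such an event would not meet this item, but it is reportable as an adverse event (D.2 leaves only Grade 1 events out of the electronic form) and would count under another item if it led to cardiogenic shock or death.
- **That the surgeon who injected decides the source.** This is plausible, but not stated.

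**Conclusion.** The point holds as a definitional weakness that is cheap to repair. The item is zero by definition in 11 of 32 subjects and rests on unspecified source attribution in the other 21. It is sound as a description of injected infants. It should not be compared between arms, nor reported over all 32, where one event reads as 3.1% instead of 4.8%. The structural zero and these two percentages follow from the documents. The 2% to 10% background rate and the 10% rate of other events are assumptions, used only for illustration. No sample size, planned test or numeric stopping rule depends on this item.

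**What to change.** Define the primary safety item as any unplanned re-operation for bleeding or tamponade in the first 5 days after Stage II, counted the same way in both arms and tabulated by arm. Record the source as injection site, other, or not identified. Report that as a descriptive sub-item in injected infants only, with a denominator of 21, and write the source criteria before the data are seen.

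The cost is the endpoint wording and one case report form field. The events should already be captured as adverse events, and sample size, treatment and visits do not change. The downside is that some bleeding unrelated to the injection enters the item in both arms, and in Group A without a control to set it against. The change also leaves the decision to re-operate with staff who may know the arm. It removes the dependence of the main count on the named source, not every effect of knowing the allocation.

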Sometimes in high-risk HLHS patients who may have severe tricuspid regurgitation or severe right ventricle dysfunction, the Stage I Norwood operation is not recommended. Instead, the Stage I Hybrid operation is preferred which uses a median sternotomy approach for pulmonary artery banding, patent ductus arteriosus stenting, and an atrial septostomy. With these Hybrid patients, the Stage II operation occurs at 4-6 months of age and involves the BDCPA operation and the Norwood operation.

The Stage II operation, the BDCPA operation, is typically performed when the HLHS patient is 4 to 6 months of age. The procedure connects the superior vena cava to the right pulmonary artery to bypass the right ventricle and allow systemic blood to flow directly to the pulmonary circulation. The second part of the BDCPA operation includes ligation of the pulmonary shunt placed during the Norwood procedure. Finally, the Stage III Fontan operation, performed when the child is between 18 months to 3 years of age, directs inferior vena caval flow into the pulmonary artery, thus bypassing the heart.

The largest and most comprehensive outcome analysis of patients undergoing a Stage I Norwood operation was reported by the Congenital Heart Surgeons' Society in 2003 (9). Between 1994 and 2000 twenty-nine institutional members of CHSS enrolled 985 neonates who had either critical aortic stenosis or atresia. A total of 710 of the 985 patients underwent a Stage I Norwood operation. The survival was 76% at 1 month, 60% at 1 year, and 54% at 5 years. Numerous studies have determined the physiologic risk factors for poor perioperative outcome after Stage I, with conflicting results (10-14). Surprisingly in these studies, right ventricular (RV) function was not reported as a predictor of survival. This is an unexpected finding since in other congenital heart surgeries for other malformations poor ventricular function has been associated with adverse outcome after operative procedures (15). Two possible explanations may exist to explain these results: 1) previous analyses of RV function in the setting of HLHS have been limited to qualitative assessment of the right ventricle, and 2) other perioperative factors in the initial unstable hemodynamic state may overshadow the impact of RV function in the early post-stage I Norwood period.

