The treated HLHS patients will receive up to 12,500 cells/kg. The terminology “up to” a certain dose indicates that if the number of the c-kit⁺ cells is not sufficiently attainable from the cardiac specimen to the specified dose then the achievable dose will be delivered. A secondary analysis of subjects who achieve ≥80% of the assigned dose will be performed as part of the overall analysis plan. The decision to weight-adjust the dose of cells was made based on preclinical studies. The cells will be delivered through 6-10 intramyocardial injections of approximately 100uL per injection for total volume of 0.6 mL

B.1.4. Premature Withdrawal

For subjects withdrawn after receiving study product injection, all efforts will be made to encourage return for all assessments through the end of the study period, so that safety can continue to be monitored.

Because the data from the proposed trial may be used to design future phases of clinical trials, we put a high priority on collecting data that is complete and accurately describes the safety and efficacy of the intervention as described. Therefore, the goal is to have final MRI and other efficacy endpoint measurements on at least 20 Group B subjects during the randomized portion of trial. As such, Group B study treatment subjects who do not undergo the stem cell injection or do not get the Stage II BDCPA operation can diminish the goal sample size of 20. A maximum of six additional subjects can be randomized to replace this potential loss to achieve the target sample size of 20 evaluable subjects.

B.2. Criteria for Subject Enrollment

B.2.1. Inclusion Criteria

For inclusion in the study, subjects must meet all of the inclusion criteria:

1. Subjects with hypoplastic left heart syndrome (all types) requiring Stage I Norwood operation.

B.2.2. Exclusion Criteria

Candidates will be excluded from the study if any of the following conditions are met:

1. Subjects undergoing the Stage I Norwood operation who do not have HLHS.
2. Subjects requiring mechanical circulatory support immediately prior to Stage II BDCPA operation (within 5 days).

3. Parent or guardian unwilling or unable to comply with necessary follow-up(s).
4. Mother is serum positive for HIV 1/2, hepatitis BsAg or viremic hepatitis C and *Treponema pallidum*.
5. Subjects who are unsuitable for inclusion in the study in the opinion of the investigator(s).

B.3 Sequence of Measurements and Evaluation

B.3.1. Subject Introduction and Informed Consent

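### Group A's ten infants are counted at enrolment, so injection safety at the DSMB review may rest on fewer than ten exposed infants and should be reported over those actually injected

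*Combined protocol and SAP*

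**What the plan says.** **Counting.** B.1.1 states "Initially in Group A, 10 consecutive HLHS patients will be enrolled" in the cell arm. B.3.2 places enrolment ahead of surgery: "The Screening Phase starts at enrollment and completes at the initiation of the harvest during the Stage I Norwood operation". B.3.3.d puts the injection at the Stage II operation, at 4 to 6 months of age.

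**Review before Group B.** B.1.1 continues: "Six months after the last patient is enrolled in Group A, the DSMB will conduct a review of all Group A patients". The review covers harvesting, processing and administering the cells. No number injected is attached to it.

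**Role and size.** B.1.2 states "The 10 Group A subjects are part of an open-label safety and feasibility analysis". For both groups together, B.1.1 says "a maximum of 21 patients will receive intramyocardial injection of" cells.

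**Replacement.** B.1.4 is concerned with "Group B study treatment subjects who do not undergo the stem cell injection or do not get the Stage II BDCPA operation". It adds: "A maximum of six additional subjects can be randomized to replace this potential loss". There is no equivalent for Group A.

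**Analysis set.** C.2 defines the Safety Analysis Set as every Group A and Group B subject and does not require injection. Primary safety and feasibility are both analysed on it. The primary safety endpoint in Section 1 is major adverse cardiac events (MACE) in the 30 days after Stage II.

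**Survival.** The only survival series after the Norwood is in the Background, from a multi-institution cohort of 1994 to 2000: "The survival was 76% at 1 month, 60% at 1 year, and 54% at 5 years". The Background also says that outcomes have improved over time.

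**The concern.** The DSMB review answers two questions with different natural denominators. Whether cells can be harvested, made and delivered is a question about everyone enrolled. Whether the injection is safe can be answered only from infants who received it. The plan gives one count, ten at enrolment, and one analysis set for both.

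Between enrolment and injection an infant may die, have no usable product, become ineligible (B.2.2 excludes infants needing mechanical support within five days before Stage II) or be withdrawn. An infant who never reaches Stage II cannot have an event in the 30 days after it, yet remains in the Safety Analysis Set. Such infants enlarge the denominator and cannot add to the numerator, so the event rate is biased downwards. This matters most at the decision to randomise 22 more infants, where a reader could take ten to be the number exposed.

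**Working it through.** **1. The plan's own figure.** The maximum of 21 injected is 10 (Group A) + 11 (Group B treated), and the total of 32 is 10 + 22. Both reproduce. The figure of 21 is reached only if every enrolled Group A infant is injected. Group B has a 10% allowance and up to six replacements; Group A has neither.

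**2. Survival to Stage II.** Inputs: 76% at 1 month and 60% at 1 year (Background); injection at 4 to 6 months (B.3.3.d). Log-linear interpolation is an assumption: S(m) = 0.76 × (0.60/0.76)^((m − 1)/11). Time after the Norwood is taken as age, since the operation falls in the first two weeks of life.

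**3. Number injected out of ten, from survival alone.** Binomial(10, p): mean 10p, P(all ten) = p^10.

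| Survival to Stage II | Expected injected | P(all ten) | P(five or fewer) |
|---|---|---|---|
| 71.3% (interpolated, 4 months) | 7.1 | 3.4% | 13% |
| 69.7% (interpolated, 5 months) | 7.0 | 2.7% | 15% |
| 68.3% (interpolated, 6 months) | 6.8 | 2.2% | 18% |
| 85% (assumed) | 8.5 | 20% | 1.0% |
| 90% (assumed) | 9.0 | 35% | 0.2% |

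The documents give no rate for product failure, ineligibility or withdrawal. If a further 10% to 20% were lost (assumption), 6.97 expected at 5 months becomes 6.97 × 0.9 = 6.3 to 6.97 × 0.8 = 5.6.

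**4. Effect on the reported rate.** Suppose seven of ten are injected and one has an event. Over the Safety Analysis Set the rate is 1/10 = 10%. Over infants injected it is 1/7 = 14.3%.

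**5. Effect on the bound when no event is seen.** The exact one-sided 95% upper bound is 1 − 0.05^(1/n).

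| Injected | Upper bound |
|---|---|
| 10 | 25.9% |
| 9 | 28.3% |
| 8 | 31.2% |
| 7 | 34.8% |
| 6 | 39.3% |

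**6. Chance of seeing at least one event.** At an assumed true 30-day rate of 10%, 1 − 0.9^n is 65% with ten injected and 52% with seven.

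**The case against.** **No promise of ten injected.** This stands. B.1.1 gives a maximum, and the review is of all Group A patients. A reader might infer that the plan undertakes to expose ten infants and falls short; the text does not say so.

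**The survival figures are old.** This also stands. The cohort is from 1994 to 2000, the Background reports improvement since, and B.3.3.a diverts high-risk infants from the Norwood to the Hybrid operation. A reader might infer that the review will rest on six to eight infants. That is a projection, and its low end uses 1-year survival, which includes deaths after the injection date. Even so, at an assumed 90% survival the chance of all ten being injected is only 35%.

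**The counting point may be later.** For Group B, B.1.1 speaks of enrolling 22 infants who are randomised after the Norwood, once viable tissue has arrived. If Group A is counted in the same way, screen failures and failed harvests are not losses from the ten. B.3.2 points to the earlier moment. Deaths between the operation and Stage II would mostly remain under either reading.

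**The asymmetry has a reason.** B.1.4 protects 20 evaluable subjects for the powered ejection-fraction comparison, and Group A has no power target. All enrolled infants are the right denominator for feasibility, and replacement must not hide manufacturing failures. This is a good argument against requiring replacement in Group A. It does not justify using the same denominator for injection safety.

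**The DSMB is not bound to proceed.** It reviews serious events as they occur, meets semi-annually and ad hoc, and can recommend stopping. Its charter was not available and may set a minimum. A reader might infer that Group B would open on five or fewer injected infants; the documents do not support that.

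**Conclusion.** The point holds for the denominator. Group A is a count of enrolled infants with no replacement rule, the review falls on a date set by enrolment, and the Safety Analysis Set mixes exposed and never-exposed infants. On the protocol's historical survival, about 7 of 10 would be injected; at an assumed 85% to 90%, 8.5 to 9, in both cases before other losses. These projections rest on survival as the main loss, independence between infants and, for the first, log-linear interpolation.

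The dilution itself needs no survival assumption. Whenever a Group A infant is not injected, a post-injection event rate over the whole set is too low. With seven injected, the rate in the example rises from 10% to 14.3% and the zero-event bound from 26% to 35%. Neither sample is precise, so the gain is an unbiased denominator and a clear statement of how little exposure lies behind the decision. It does not turn a weak safety sample into a strong one.

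**What to change.** 1. **B.1.1:** state that ten is the number enrolled in Group A and not the number exposed. If the sponsor and DSMB set a minimum number injected before Group B opens, refer to it here.
2. **C.2:** keep all enrolled Group A infants for feasibility, and add a set of infants actually injected for injection safety.
3. **C.3:** report injection safety and 30-day MACE over infants injected, at the DSMB review and in the final analysis, each time with the number injected and its exact confidence bound.

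The cost is wording in three sections and a smaller, less favourable denominator. No extra enrolment is required. A projected number injected should not be written into the protocol, since the only cited survival series is dated.
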